5.3 Prohibited medications

Table 5-9 Prohibited medication with respective ATC codes

Prohibited medication	ATC code	ATC name
ANALGESICS	N02CC06	Eletriptan
	N02CA01	Dihydroergotamine
	N02CA02	Ergotamine
ANESTHETICS	N02AB03	Fentanyl
	N01AH02	Alfentanil
	N01AH01	Fentanyl
ANTIARRHYTHMICS	C01BD07	Dronedarone
	C01BC04	Flecainide
	C01BA01	Quinidine
	N06AA01	Desipramine
	N06AX16	Venlafaxine
	N06AX12	Bupropion
	N06AA02	Imipramine
ANTIEMETICS AND ANTINAUSEANTS	N06AA09	Amitriptyline
	N06AA04	Clomipramine
	A04AD12	Aprepitant
	N03AB02	Phenytoin
ANTIEPILEPTICS		
ANTIHISTAMINES FOR SYSTEMIC USE	R06AX11	Astemizole
	R06AX12	Terfenadine
ANTIINFLAMMATORY AND ANTIRHEUMATIC PRODUCTS	M01AH01	Celecoxib
ANTINEOPLASTIC AGENTS	L01CD01	Paclitaxel
ANTIPSYCHOTICS	N05AB03	Perphenazine
	N05AE05	Lurasidone
	N05AH04	Quetiapine
	N05AC02	Thioridazine
	N05AG02	Pimozide
	N05	Neuroleptics
ANTITHROMBOTIC AGENTS	B01AA03	Warfarin
ANXIOLYTICS	N05BE01	Buspirone
BETA BLOCKING AGENTS	C07AB02	Metoprolol
	C07AB12	Nebivolol
	C07AB02	Metoprolol
CALCIUM CHANNEL BLOCKERS	C08CA02	Felodipine
	C08CA07	Nisoldipine
CORTICOSTEROIDES	R01AD08	Fluticasone
COUGH SUPPRESSANTS	R05DA09	Dextromethorphan
DIRECT ACTING ANTIVIRALS	J05AE10	Darunavir
	J05AE02	Indinavir
	J05AR10	Lopinavir
	J05AX09	Maraviroc

	J05AE01	Saquinavir
	J05AE09	Tipranavir
	J05AG03	Efavirenz
DIURETICS	C03DA04	Eplerenone
	C03XA01	Tolvaptan
DRUGS FOR FUNCTIONAL GASTROINTESTINAL DISORDERS	A03FA02	Cisapride
HYPNOTICS AND SEDATIVES	N05CD08	Midazolam
	N05CD05	Triazolam
IMMUNOSUPPRESSANTS	L04AA18	Everolimus
	L04AA10	Sirolimus
	L04AD01	Ciclosporin
	L04AA10	Sirolimus
	L04AD02	Tacrolimus
INTESTINAL ANTIINFLAMMATORY AGENTS	A07EA06	Budesonide
LIPID MODIFYING AGENTS	C10AA02	Lovastatin
	C10AA01	Simvastatin
	C10AA03	Pravastatin
OTHER ANTIHYPERTENSIVES	C02KX01	Bosentan
OTHER ANTINEOPLASTIC AGENTS	L01XE06	Dasatinib
	L01XE10	Everolimus
	L01XX33	Celecoxib
OTHER BLOOD GLUCOSE LOWERING DRUGS	A10BX02	Repaglinide
OTHER DERMATOLOGICAL PREPARATIONS	D11AH01	Tacrolimus
OTHER DIURETICS	C03XA02	Conivaptan
OTHER OPHTHALMOLOGICALS	S01XA18	Ciclosporin
	S01XA23	Sirolimus
PSYCHOSTIMULANTS	N06BA09	Atomoxetine
UROLOGICALS	G04BD07	Tolterodine
	G04BD10	Darifenacin
	G04BE03	Sildenafil
	G04BE09	Vardenafil

5.4 AEs coding/grading

Adverse events are coded using the Medical dictionary for regulatory activities (MedDRA) terminology. AEs are assessed by [investigators](#) according to the most current Common Terminology Criteria for Adverse Events (CTCAE) version [4.0](#)

5.5 Laboratory parameters derivations

Grade categorization of lab values will be assigned programmatically as per NCI Common Terminology Criteria for Adverse Events (CTCAE) version [4.0](#) (specify version used in the

RAP). The calculation of CTCAE grades will be based on the observed laboratory values only, clinical assessments will not be taken into account. The criteria to assign CTCAE grades are given in Novartis internal criteria for CTCAE grading of laboratory parameters. The latest available version of the document based on the underlying CTCAE version 4.0 at the time of analysis will be used.

A severity grade of 0 will be assigned for all non-missing lab values not graded as 1 or higher. Grade 5 will not be used. For laboratory tests that are graded for both low and high values, summaries will be done separately and labelled by direction, e.g., sodium will be summarized as hyponatremia and hypernatremia.

5.6 Statistical models

5.6.1 Primary analysis

The primary analysis of ACPR at Day 29 is detailed in [Section 2](#).

SAS procedure FREQ with EXACT statement for one-way tables will be used to estimate the proportion of responders (binary outcome = 1 or “Yes”), along with the associated 95% ($=100 \times (1 - \text{two-sided } \alpha \text{ level})$) two-sided Clopper- Pearson CI [[Clopper and Pearson 1934](#)].

5.6.2 Key secondary analysis

NA

5.6.3 Other secondary XXXXXXXXXX analysis

Kaplan-Meier estimates

An estimate of the survival function in each treatment group will be constructed using Kaplan-Meier (product-limit) method as implemented in PROC LIFETEST with METHOD=KM option. The PROC LIFETEST statement will use the option CONFTYPE=LOGLOG.

Median survival for each treatment group will be obtained along with 95% confidence intervals calculated from PROC LIFETEST output using the method of [[Brookmeyer and Crowley 1982](#)]. Kaplan-Meier estimates of the survivor function with 95% confidence intervals at specific time points will be summarized. The standard error of the Kaplan-Meier estimate will be calculated using Greenwood’s formula [[Collett 1994](#)].

Difference in responder rates stratified by part using Mantel-Hanszel estimate

For PCR corrected and uncorrected ACPR rates, the treatment differences versus control will be evaluated using a Mantel-Haenszel estimate of the treatment difference in responder rates stratified by Part using PROC FREQ with RISKDIFF(COMMON) option in the TABLES statement).

Difference in responder rates using the Wilson uncorrected method

For PCR corrected and uncorrected ACPR rates, the treatment differences versus control will be evaluated using a Wilson uncorrected method using PROC FREQ with RISKDIFF (CL=WILSON) option in the TABLES statement.

5.7 Rule of exclusion criteria of analysis sets

Table 5-10 Protocol deviations and non-PD criteria leading to exclusion from analysis sets

Analysis Set	PD (Description and ID) that causes Patients to be excluded	Non-PD criteria that cause Patients to be excluded
Randomized	
 Informed Consent for study participation or parental consent not obtained and patient entered trial (INCL01) 	
 Not randomized (Parts A and B) Misrandomized if identified from IRT (Parts A and B) Not treated with study medication (PK run-in part)
FAS	NA	
 Not in Randomized set; Baseline parasitemia count is 0 or missing No study drug taken
PPS	
 Parasite specie is other than Plasmodium falciparum OR mixed infection (INCL04) Baseline plasmodium falciparum parasite count <1000/uL or >=150000/uL at screening visit (INCL05) No fever within the past 24 hours at baseline (INCL07) Prohibited non-antimalarial medications that may have effect on efficacy (PROH01b) if received before the Day 29 visit without being treatment failures 	
 Not in FAS; <80% of randomized study medication taken Received non-study concomitant antimalarial drugs prior to Day 29 without experiencing treatment failure Not classified as non-responder before Day 8, no positive blood smear parasite on Day 8 onwards, and blood smear parasite result is missing at Day 29 and later (early discontinued) Not classified as non-responder before Day 8, have at least one positive blood smear parasite result between Day 8 and Day 29 which cannot be determined as recrudescence or new infection based on PCR genotyping and have parasites cleared prior to the positive blood smear parasite;

		
 Not classified as non-responder before Day 8, no positive blood smear parasite before Day 29, blood smear parasite result is missing at Day 29, and blood smear parasite result is not negative at Day 43 (intermediate missing)
SAF	NA	
 Not in Randomized set; No study drug taken
PK	Patients who received concomitant prohibited medication which found to be change in the exposure that impacts interaction in PK parameters; will be reviewed case by case for exclusion from the PK set	
 Not in SAF No evaluable pharmacokinetic parameter data Compliance is <80% of randomized study medication taken

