### 5.7.2 Discontinuation of study treatment

Patients will be treated under hospital supervision during the treatment period. Discontinuation of study treatment for a patient occurs when study drug is stopped earlier than the protocol

planned duration, and discontinuation can be initiated by either the patient or the investigator. For patients assigned to 1-day and 2-day cohorts, they will not be considered as treatment discontinuation if those discontinuation events occur after they have completed the treatment as assigned.

The investigator must discontinue study treatment for a given patient if, on balance, he/she believes that continuation would negatively impact the patient's risk of trial participation.

Study treatment must be discontinued under the following circumstances:

[figure not shown]
- Patient request
- Pregnancy (see [Section 6.5.6](#) and [Section 7.7](#))
- Use of prohibited treatment as per recommendations in [Table 5-5](#)
- Any situation in which study participation might result in a safety risk to the patient and/or any adverse events that in the judgment of the investigator, taking into account the patient's overall status, prevent the patient from continuing participation in the study
- Unsatisfactory therapeutic effect (see [Section 6.5.8](#))
- Emergence of the following adverse events: severe nausea/vomiting, severe pruritus, increases in QTcF to > 500 ms (based on repeat ECGs), development of ventricular arrhythmia or clinically significant (symptomatic) bradycardia (see [Appendix 3](#))
- Any laboratory abnormalities that in the judgment of the investigator, taking into consideration the patient's overall status, prevent the patient from continuing participation in the study (e.g., increase in liver enzymes > 3 times the upper limit of normal (see [Appendix 2](#)))
- Deviation from the planned dose regimen for the study drug (e.g., vomiting of the replacement dose within 2 hours of intake)

Patients who discontinue study drug for any of the above reasons may be given rescue medication at the discretion of the investigator and will be followed for the whole study duration until Day 43.

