## PK analysis set

All subjects in the safety analysis set who had evaluable pharmacokinetic parameter data.

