- met at least one of the following criteria: (a) classified as treatment failure (including parasite not cleared) before Day 8 (see [Section 2.1.1](#)), (b) absent from parasitemia at Day 29 or later, (c) had valid PCR evaluations at baseline and at the time point with parasitemia using malaria blood film if parasitemia is present between Day 8 and Day 29, or (d) had parasitemia present on Day 8 or later without parasite clearance before Day 8.

Important protocol deviations for exclusion from PPS are specified in [Table 5-9](#) and will be identified by the clinical team before database lock for each part.

PK analysis set

All patients in the safety analysis set who had evaluable pharmacokinetic parameter data and with at least 80% compliance to study medication and did not receive the concomitant prohibited medication which found to be change in the exposure that impacts interaction in PK parameters.

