2.4 Treatments (study treatment, rescue medication, concomitant therapies, compliance)

2.4.1 Study treatment / compliance

Number and percent of doses taken will be presented by treatment group and drug (KAF156, LUM-SDF, or Coartem[®]). The percentage will be calculated based on the planned number of doses per treatment group.

Planned number of doses in a treatment group = planned number of days of dosing x number of doses to be administered per day in that treatment group.

For example, planned number of doses is 3 for 'KAF156 400 mg and LUM-SDF 480 mg QD for 3 days' group, 6 for Coartem, etc.

In the percent calculation for KAF156/LUM-SDF based treatment groups, patient is considered to be dosed if s/he took any study drug regardless of vomiting or not.

Percent of doses taken (i.e. compliance) on a day will be calculated as actual dose administered /planned dose x 100% capped at 100% (if a compliance on a given day exceeds 100%, use 100%). Average compliance for a study drug will be calculated as sum of the compliance for all days and divide by the number of day's. For KAF/LUM, compliance for combined dose will be the average compliance of both drugs.

In addition, percent of full doses taken will be calculated as actual number of full doses administered /planned number of doses x 100% where a patient is considered to be fully dosed if s/he took all study drug(s) in full dose.

Compliance will be categorized by < 80 % and \geq 80 % of full doses taken and summarized by treatment group.

Number and percent of patients with study drug vomiting and dose replacement will be presented by treatment group.

Average daily dosage and total dosage (in mg) of each study drug (KAF156, LUM-SDF, Artemether, Lumefantrine) will be summarized by treatment group. If a patient vomited the original dose and took a replacement dose, the replacement dose will be used to calculate the average.

Average daily dosage = sum of actual doses taken in mg / **planned number of days of treatment**.

For Coartem, the tablets taken by the patient are converted into mg based on the strength of tablet.

Note- If a patient vomited the original dose but did not vomit the replacement dose, the patient is considered as fully dosed. If a patient vomited the original dose and did not have a replacement dose or vomited both the original dose and the replacement dose, the patient is not considered as fully dosed.

Safety set will be used.

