2.8.3 Other safety data

2.8.3.1 ECG and cardiac imaging data

The following quantitative variables will be summarized for averaged triplicate ECG: heart rate, RR interval, PR interval, QRS interval, QT interval, QTcB (QT interval corrected for heart rate according to Bazett) and QTcF (QT interval corrected for heart rate according to Fredericia).

Descriptive summary statistics for the change from baseline for each post-baseline visit will be performed by ECG parameters and treatment group.

Patients with notably high QT, HR and fever ($\geq 37.5^\circ\text{C}$ for *axillary* or $\geq 38.3^\circ\text{C}$ for other routes) will be provided.

To assess the temporal correlations mean change of QTcF over time, mean change of ECG HR over time, mean change of temperature over time, and PK concentration of KAF156 and lumefantrine over time will be plotted with all panels aligned on the x-axis (Time after dosing).

QTc will be summarized categorically by computing the number and percentage of patients at each time point and at the maximum post baseline value with following:

- QT, QTcF, or QTcB
 - > 450 and ≤ 480 ms
 - > 480 and ≤ 500 ms
 - > 500 ms
 - Increase from Baseline of ≥ 30 ms to < 60 ms
 - Increase from Baseline of ≥ 60 ms
- HR for age ≥ 18 years
 - Increase from baseline $>25\%$ and to a value > 100 bpm
 - Decrease from baseline $>25\%$ and to a value < 50 bpm
- HR for age < 18 years
 - $>$ upper limit of normal (ULN) defined in Table 2-3
 - $<$ lower limit of normal (LLN) defined in Table 2-3
- PR

- Increase from baseline >25% and to a value > 200 ms
- New value of > 200 ms
- QRS
 - Increase from baseline >25% and to a value > 120 ms
 - > 120 ms

Table 2-3 Normal heart rates (resting) by age

Age (years)	Normal range bpm
1 - ≤ 3	70 - 110
3 - ≤ 6	65 -110
6 - ≤12	60 -95
>12	55 -85

Source: Nelson Textbook of Pediatrics, 18th Edition

A line plot by patient (Spaghetti plot) will be provided by visit and treatment group.

In addition, shift tables comparing baseline ECG results (normal, abnormal, not available, total) with the post-baseline results will be provided by visit and at the worst post-baseline result (normal, abnormal, not available, total).

A listing of all newly occurring or worsening abnormalities as compared with baseline will be provided, as well as a by-patient listing of all quantitative ECG parameters.

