Assuming that about 16% of patients will be excluded from the per-protocol analysis set, about 325 patients (50:50:50:50:50:25) will be randomized to yield 42 patients for each KAF156/LUM-SDF dose combinations and 21 patients for the Coartem[®] cohort in the per-protocol analysis set.

Figure 3-1 Power to reject adequate clinical and parasitological response (ACPR) rate less than or equal to 80% based on 2-sided 95% CI by true rate

Part B

The primary objective for this part is to assess the safety and efficacy of the selected KAF156/LUM-SDF dose combination(s) adjusted for body weight in pediatric patients. For the primary efficacy variable of PCR corrected ACPR rate at Day 29 based on the per-protocol analysis set, a sample size of at least 41 patients will provide about 80% power or higher to reject the null hypothesis of at most 80% ACPR rate based on the lower limit of 2-sided 95% exact confidence interval if the true rate is 95% or higher for a KAF156/LUM-SDF dose combination. Since there is a 2:1 ratio between a KAF156/LUM-SDF dose combination group and the Coartem[®] cohort, the sample size in the per-protocol analysis set will be targeted to be 42 patients for each KAF156/LUM-SDF dose combination group and 21 patients for the Coartem[®] cohort. Assuming that 16% of patients will be excluded from the per-protocol analysis set, about 50 pediatric patients will be randomized to yield 42 patients for each KAF156 and LUM-SDF combination and 21 patients for the Coartem[®] cohort in the per-protocol analysis set.

4 Change to protocol specified analyses

None

5 Appendix

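### The SAP adds an undeclared 80% compliance rule to the PK set, which discards complete first-dose profiles of multi-day rich-PK patients who stop early

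*SAP*

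**What the plan says.** Protocol Section 9.1 defines the PK set as "All subjects in the safety analysis set who had evaluable pharmacokinetic parameter data". It sets no compliance threshold.

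SAP Section 2.2 narrows this to patients "who had evaluable pharmacokinetic parameter data and with at least 80% compliance to study medication". Table 5-10 in SAP Section 5.7 repeats the rule as a ground for exclusion: "Compliance is <80% of randomized study medication taken". Both act on the patient, so all parameters go together. Table 5-10 also provides for case-by-case removal of "Patients who received concomitant prohibited medication which found to be change in the exposure that impacts interaction in PK parameters".

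SAP Section 2.4.1 defines compliance: "Average compliance for a study drug will be calculated as sum of the compliance for all days and divide by the number of day's". For KAF156/LUM-SDF the two drugs are then averaged.

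The SAP revision history records the compliance rule under 10 March 2019. Section 4, headed "Change to protocol specified analyses", nevertheless says there are none.

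SAP Section 2.9 gives 90% confidence intervals for AUC0-24h, Cmax and Tmax by part and treatment group. Table 2-8 names the PK set for the PK output reviewed at the end of Part A.

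**The concern.** A missed second or third dose cannot alter what was measured in the 24 hours after the first. The rule still removes that measurement along with everything else from the patient.

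The removal need not be random. Protocol Section 5.7.2 lists among its reasons for stopping "increases in QTcF to > 500 ms (based on repeat ECGs"), ventricular arrhythmia, symptomatic bradycardia, severe vomiting and unsatisfactory effect. Section 6.5.5 ties a QTc stop specifically to 2-3 day regimens with a dose still to come. Some of these reasons may go with high exposure and others with low exposure. The non-compartmental summaries by regimen could therefore lack patients from either tail. Those summaries form part of the evidence laid out when regimens are chosen for children.

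Separately, a reader comparing the protocol with SAP Section 4 would not learn that the set had changed.

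**Working it through.** **1. The plan's own PK figure.** Protocol Table 9-1 and SAP Table 3-1 state that with n = 12 and SD of log AUC0-24h 0.26, the observed 90% CI half-width is at most 0.155 with probability 0.80.
- Formula: P = chi-square CDF on n−1 df at (n−1)·(w·√n / (t·SD))², with t = t(0.95, n−1).
- Here t(0.95, 11) = 1.796, so the argument is 11·(0.155·3.464 / (1.796·0.26))² = 14.5 and P = 0.796.
- The stated figure is reproduced, so SD 0.26 is used below.

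**2. Compliance at an early stop.** The SAP does not say whether the divisor is planned or actual days. Planned days are assumed. This fits the reference to randomised medication in Table 5-10 and the planned-dose denominator used elsewhere in Section 2.4.1.
- 2-day regimen stopped after dose 1: 1/2 = 50%.
- 3-day regimen stopped after dose 1: 1/3 = 33%. After dose 2: 2/3 = 67%.
- 1-day regimen, full dose: 100%.

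Every stop before the last dosing day in Cohorts 3-6 is therefore below 80%.

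**3. Who has a complete first-dose profile to lose.** Protocol Table 6-3 samples rich-PK patients on 2- and 3-day regimens at 0, 1, 3, 6, 12 and 24 h.
- Planned rich PK in Part A (Protocol Section 3.1): 6+6+6+6+12+6 = 42.
- Of these, Cohorts 3-6: 6+6+12+6 = 30.
- Planned randomised in Cohorts 3-6: 4 × 50 = 200, so 200 − 30 = 170 are sparse. In the first 24 h they give samples at 3, 6 and 24 h only. In Part B, multi-day patients give only the 24 h sample in that interval (Table 6-4).

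**4. Precision.** Typical 90% half-width on the log scale = t(0.95, n−1)·0.26/√n.
- n = 6: 2.015·0.26/2.449 = 0.214, ratio 1.24.
- n = 5: 2.132·0.26/2.236 = 0.248, ratio 1.28.
- n = 12 (Cohort 5): ratio 1.14. n = 10: ratio 1.16.

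**5. Possible shift in the geometric mean.** The documents give no stopping rate and no link between stopping and exposure, so both are assumed. Let a fraction d stop, and let ρ be the correlation between the tendency to stop and log exposure. The mean of those kept is multiplied by exp(−ρ·0.26·φ(z)/(1−d)), where z is the 1−d normal quantile. The upper end of d is the 16% drop-out rate in Protocol Section 4, which is not a treatment-stopping rate and serves only as a bound.

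| Assumed stopped | ρ = 0 | ρ = 0.5 | ρ = 1 |
|---|---|---|---|
| 2% | 0% | −0.6% | −1.3% |
| 5% | 0% | −1.4% | −2.8% |
| 10% | 0% | −2.5% | −4.9% |
| 16% | 0% | −3.7% | −7.3% |

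Patients stopped for early failure with low exposure would move the mean the other way.

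**The case against.** A compliance rule has a clear rationale for AUCinf, AUClast, last-dose Cmax and the 168 h concentration, because a patient who took one dose of three does not represent the regimen. Restoring the protocol set without further conditions would mix incomplete regimens into those summaries. This stands, and it shapes the fix. Cmax is also not stated to be first-dose Cmax, so only AUC0-24h is plainly a first-dose quantity.

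The triggers are narrower than the list of stopping reasons suggests. A patient who vomits both the first dose and its replacement has no valid first-dose profile to lose. Early failure counts only on Days 2-3, since the Day 4 criteria fall after all dosing. Both limits stand.

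The data are not lost altogether. Concentrations are listed, and SAP Section 2.9 allows all PK data to be pooled for population PK.

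Three stronger readings are tempting but not supported:
- *The aligned QTcF and PK plot shows different patients in its panels.* SAP Section 2.8.3.1 says that "PK concentration of KAF156 and lumefantrine over time will be plotted with all panels aligned on the x-axis" but names no analysis set. Section 2.8 places all safety analyses on the safety set.
- *The PK set drives the choice of Part B regimens.* Protocol Section 3.5 says PK data alone will not change study conduct. Table 3-2 rests selection on the ACPR lower limit and a safety assessment. PK is one input.
- *The co-medication rule is applied after seeing the patient's own concentrations.* The sentence is garbled and can equally mean drugs known to alter exposure, such as those in Protocol Section 5.6.8.2. It needs rewording, but it does not establish selection on the result.

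**Conclusion.** The point holds in limited form. The added threshold is a change from the protocol that SAP Section 4 should declare, whatever its numerical effect. The loss of a complete first-dose AUC0-24h and peak is confined to rich-PK patients in Cohorts 3-6 who stop before their last dose. That is at most 30 of 42 planned, and the number who will stop is not given.

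Selection on exposure or its consequences is possible, but its size and direction cannot be derived from the documents. The range of 0 to about 7% is conditional on the assumptions in step 5. The wider interval after losing one of six is a loss of precision that would follow from any missing patient, and is not itself evidence of bias. A larger shift in a cohort of six would require the lost patient to be the most extreme, and nothing in the documents supports assuming that.

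A reader might also infer that the run-in AUC0-24h comparison, which sets Part A dosing, is compromised. It is not: the run-in is a single-dose cohort, as are Cohorts 1 and 2, so there is no later dose to stop. Sparse-PK multi-day patients lose only partial data. The conclusion assumes planned days as the compliance divisor. If actual dosing days were meant, a patient stopped after a full first dose would score 100% and stay in the set.

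**What to change.** - Replace the patient-level compliance exclusion with parameter-level evaluability. Keep first-dose AUC0-24h, Cmax and Tmax for any patient who took and retained the full first dose and was sampled to 24 h. Apply the 80% criterion only to full-regimen parameters such as AUCinf, AUClast, last-dose Cmax and the 168 h concentration.
- State in SAP Section 2.9 whether each Cmax and Tmax is first-dose or last-dose, and in Section 2.4.1 that the compliance divisor is planned days.
- Reword the co-medication exclusion to refer to drugs known to alter exposure, such as the CYP3A inhibitors and inducers in Protocol Section 5.6.8.2, and have it decided before concentrations are reviewed.
- List PK exclusions by reason and treatment group, and record the change in SAP Section 4.

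The cost is SAP wording, an extra flag in the PK dataset and tables whose n differs by parameter. No new samples are needed.
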